**3.0**

**LIST OF ABBREVIATIONS**

AE	adverse event
AESI	adverse event of special interest
ALT	alanine aminotransferase
ALP	alkaline phosphatase
ANCOVA	analysis of covariance
AST	aspartate aminotransferase
ATH	Armour Thyroid
CFB	change from baseline
CDF	cumulative distribution function
CI	confidence interval
CMH	Cochran-Mantel-Haenszel
eCRF	electronic case report form
ECG	electrocardiogram, electrocardiographic
EOT	end of trial
ITT	intent to treat
MAR	missing at random
MI	multiple imputation
OC	observed cases
PCS	potentially clinically significant
QTc	QT interval corrected for heart rate
QTcB	QT interval corrected for heart rate using the Bazett formula ( $QTcB = QT/(RR)^{1/2}$ )
QTcF	QT interval corrected for heart rate using the Fridericia formula ( $QTcF = QT/(RR)^{4/5}$ )
RM	rescue medication
SAE	serious adverse event
SAP	statistical analysis plan
SE	standard error
SI	Le Système International d'Unités (International System of Units)
SOC	system organ class
TBL	total bilirubin
TEAE	treatment-emergent adverse event
TESAE	treatment-emergent serious adverse event

## **4.0**

## **INTRODUCTION**

This statistical analysis plan (SAP) provides technical and detailed elaboration of the statistical analyses of the efficacy and safety data that will be performed for Study 3014-201-002 as outlined and/or specified in a final protocol dated 28 May 2019 and the most recent amendment dated 16 Jan 2020. Specifications of tables, listings and figures are provided in a separate document.

### **4.1**

### **STUDY DESIGN:**

Study 3014-201-002 is a randomized, double-blinded, parallel-group, active-controlled, multicenter, dose-conversion study in previously hypothyroid participants, who are euthyroid on a stable dose of T4 replacement therapy, to evaluate the efficacy and safety of replacement therapy with matching doses of Armour Thyroid in comparison to synthetic T4.

During the coronavirus disease 2019 (COVID-19) pandemic, the mitigation strategy of increasing enrollment has been implemented to overcome the loss of information from the impact of COVID-19. Approximately 284 total participants (an increased enrollment from the original planned sample size of 220 participants specified in the protocol) who meet eligibility criteria will be randomly assigned to study intervention in a 1:1 ratio (approximately 142 participants per arm), stratified by age (< 65 years,  $\geq$  65 years).

The study will last approximately 33 to 51 weeks (with a planned minimum of 7 visits and a maximum of 15 possible visits if participants require additional dose titration) and will include a Screening Period (up to 3 weeks), double-blinded Titration Period (at least 18 weeks), and a double-blinded Stabilization Period (12 weeks).

[figure not shown]
All participants entering the study will be controlled on a stable, FDA-approved, daily dose of synthetic T4 (i.e., euthyroid) for at least 3 months and will be randomized to either the same dose of synthetic T4 or a matching dose of Armour Thyroid during the first visit of the Titration Period (Visit 2). For each available dose of synthetic T4, up to 200  $\mu$ g, a matching dose of Armour Thyroid will be employed according to a dose-conversion table based on the USP Drug Information 2000. Armour Thyroid and synthetic T4 will be administered as a single oral dose of 2 capsules (one of these capsules may be placebo), once-daily, on an empty stomach at least 30 to 60 minutes before the first meal. Serum TSH levels will be measured prior to study intervention administration during study visits.

During the Titration Period, participants will continue the same dose taken during the last visit or have their dose up- or down-titrated as needed per the Investigators' interpretation of their TSH levels (normal reference range 0.45-4.12 mIU/L, inclusive). For example, Investigators should up-titrate the dose if the TSH value is above 4.12 mIU/L and down-titrate the dose if the TSH value is below 0.45 mIU/L during the Titration Period. Other thyroid-related assessments and evaluation of thyroid clinical status will also be completed.

Investigators may only titrate participants' doses, as needed, until the start of the Stabilization Period. Participants will remain on a stable dose during the Stabilization Period until the end of the study.

Study schematic and schedule of evaluation are presented in [Figure 4-1](#) and [Table 4-1](#) respectively

**Figure 4-1**      **3014-201-002 Study Schematic**

\* If a participant undergoes up to the maximum of 3 additional dose titrations starting at Week 18, the Titration Period may extend up to Week 36; therefore, the Stabilization Period may extend from Week 36 to Week 48 (remaining 12 weeks in duration). The Primary Endpoint will be measured at the end of the Titration Period and the end of the Stabilization Period.

During the Titration Period, study visits are split into parts A and B (i.e., Visit 3a, Visit 3b, Visit 4a, Visit 4b) to allow for any dose titrations:

- Visits 3a and 4a are mandatory for all participants. Study assessments, including bloodwork for total T3, TSH, and study intervention dispensing will be performed.
- Visits 3b and 4b are only required for participants needing a dose titration based on the data obtained from Visits 3a and 4a, respectively. A limited number of assessments and study intervention dispensing will be performed.

Visit 5 is designed as a transition visit between the Titration and Stabilization Periods and may consist of a subset of visits (starting with Visit 5a [Week 18] and extending to Visit 5g [Week 36], as needed). The last visit within Visit 5 serves as both the end of the Titration Period and the beginning of the Stabilization Period.

- Participants with TSH levels within normal reference range at Visit 5a may enter the Stabilization Period (i.e., their next visit will be Visit 6).
- If participants' TSH levels are out of normal reference range at Visit 5a, participants' doses can be up- or down-titrated per the Investigators' interpretation until their TSH levels are within the normal reference range by continuing the Titration Period

beyond Week 18. If the Titration Period is continued, the participants' doses can be up- or down-titrated approximately every 6 weeks until their TSH levels have normalized for up to a maximum of 3 additional titrations (including the titration at Visit 5b). Once their TSH levels are within the normal reference range, participants can enter the Stabilization Period. Participants whose TSH levels have not normalized after the maximum of 3 additional titrations will not enter the Stabilization Period.

- Participants who need dose titration beyond Week 18 will complete a study visit approximately every 6 weeks to determine if their TSH levels are within the normal reference range. At these visits, they will have the same assessments performed as those performed at Visit 5a including study intervention dispensing. These assessment visits will be labeled sequentially 5c (Week 24), 5e (Week 30), and 5g (Week 36), as needed.
- Participants who need dose titration beyond Week 18 will also complete a study visit for additional study intervention dispensing. These study intervention visits will be labeled sequentially as 5b (Week 19), 5d (Week 25), and 5f (Week 31), as needed. Visit 5d and 5f will have all the same assessments and activities performed as Visit 5b.

The Titration Period is at least 18 weeks in duration. Depending on whether a participant requires additional dose titration after Visit 5a, the Titration Period may end at Week 18, 24, 30, or 36 (up to a maximum of 3 additional titrations are allowed starting at Visit 5b).

The Stabilization Period is 12 weeks in duration. Depending on whether a participant requires additional dose titration after Visit 5a, the Stabilization Period may end at Week 30, 36, 42, or 48. If a participant undergoes the maximum of 3 additional dose titrations starting at Week 5b, the Stabilization Period would be from Week 36 to Week 48.

Visit 6 may be at Week 24, 30, 36, or 42 depending on the number of additional titrations needed after Visit 5a. Visit 7 may be at Week 30, 36, 42, or 48 depending on the number of additional titrations needed after Visit 5a.

**Table 4-1** Schedule Activities

3014-201-002 Schedule of Activities											
	Screening	Titration Period (Week 0 to Week 18 a )							Stabilization Period (Week 18 a to Week 30 c )		Early Termination
		Visit 1	Visit 2	Visit 3a	Visit 3b d	Visit 4a	Visit 4b d	Visit 5a e	Visit 5b d,e	Visit 6 f	Visit 7 g
Visit Number	Visit 1										
Study Week	-3 to 0	0	6	7	12	13	18 d	19	24	30	
Visit Window	---	±3 days	±3 days	±3 days	±3 days	±3 days	±3 days	±3 days	±3 days	±3 days	
Informed consent	X										
Randomization		X									
Inclusion/exclusion	X	X									
Demographic data	X										
Medical history	X										
AEs	X	X	X	X	X	X	X	X	X	X	X
Clinical laboratory b,h,n	X	X	X		X		X		X	X	X
Vital signs b,i	X	X	X	X	X	X	X	X	X	X	X
ECG b	X	X	X		X		X		X	X	X
Physical examination j	X									X	X
BMI	X									X	X
Urine pregnancy test b (females of CBP)		X	X		X		X		X	X	X
Serum pregnancy test (females of CBP) b,n	X	X	X		X		X		X	X	X
Serum TSH, T4, T3, FT3, FT4 (Thyroid-related assessments) b,n	X	X	X		X		X		X	X	X
Thyroglobulin and anti-thyroglobulin n,o	X										
PK blood samples k,n		X								X	
Thyroid symptom questionnaire (ThyPRO Questionnaire)	X	X	X		X		X		X	X	
Concomitant medications	X	X	X	X	X	X	X	X	X	X	X

	Screening	Titration Period (Week 0 to Week 18 a )							Stabilization Period (Week 18 a to Week 30 c )			Early Termination
		Visit 1	Visit 2	Visit 3a	Visit 3b d	Visit 4a	Visit 4b d	Visit 5a e	Visit 5b d,e	Visit 6 f	Visit 7 g	
Visit Number	Visit 1	Visit 2	Visit 3a	Visit 3b d	Visit 4a	Visit 4b d	Visit 5a e	Visit 5b d,e	Visit 6 f	Visit 7 g	ET	
Study Week	-3 to 0	0	6	7	12	13	18 d	19	24	30		
Visit Window	---	±3 days	±3 days	±3 days	±3 days	±3 days	±3 days	±3 days	±3 days	±3 days		
Evaluation of thyroid clinical status l	X	X	X		X		X		X	X	X	
Study intervention dispensing		X	X	X	X	X	X	X	X			
Study intervention compliance		X m	X	X	X	X	X	X	X	X	X	
Study intervention collection			X	X	X	X	X	X	X	X	X	X
Potential for dose adjustment				X		X		X				

AE = adverse event; BMI = body mass index; BP = blood pressure; CBP = childbearing potential; ECG = electrocardiogram; ET = early termination; FT3 = free T3; FT4 = free T4; IRB/IEC = institutional review board/independent ethics committee; PK = pharmacokinetic; T3 = liothyronine; T4 = levothyroxine; TSH = thyroid-stimulating hormone

a The Titration Period is at least 18 weeks in duration. Depending on whether a participant requires additional dose titration after Visit 5a, the Titration Period may end at Week 18, 24, 30, or 36 (up to a maximum of 3 additional titrations are allowed starting at Visit 5b).

b These assessments will be pre-dose.

c The Stabilization Period is 12 weeks in duration. Depending on whether a participant requires additional dose titration after Visit 5a, the Stabilization Period may end at Week 30, 36, 42, or 48. If a participant undergoes the maximum of 3 additional dose titrations starting at Week 5b, the Stabilization Period would be from Week 36 to Week 48.

d This study intervention dispensing visit is only applicable to participants needing a dose titration.

e Visit 5 is designed as a transition visit, which serves as both the end of the Titration Period and the beginning of the Stabilization Period. At Visit 5a (Week 18), if a participant's TSH level is not within normal reference range, the participant may have his/her dose up- or down-titrated per the Investigator's interpretation of his/her TSH level by continuing the Titration Period beyond Week 18 for additional visits, as needed. The additional study intervention dispensing visits will be labeled sequentially (Visit 5b, 5d, and 5f, as needed). Visit 5d and 5f will have all the same assessments and activities performed as Visit 5b. Additional assessment visits will be labeled sequentially (Visit 5c, 5e, 5g, as needed), and will have all the same assessments and activities performed as Visit 5a.

f Visit 6 may be at Week 24, 30, 36, or 42 depending on the number of additional titrations needed after Visit 5a.

g Visit 7 may be at Week 30, 36, 42, or 48 depending on the number of additional titrations needed after Visit 5a.

h Hematology, chemistry, urinalysis.

i BP, pulse rate; respiratory rate, and oral temperature

j Includes height and weight measurements (height at Screening Visit only)

k PK samples will be collected pre-dose and 2 hour (± 30 minutes) post-dose at Visits 2 and 7. Additionally, the date and time of dose on the day of PK sampling will be recorded.

l This includes evaluation of hypothyroid symptoms, which will be documented in the eCRF.

m Compliance assessment at Visit 2 relates to the participant having taken his/her own synthetic T4 between Visit 1 and Visit 2.

n Participants will be required to undergo an overnight (minimum 5 hours) fast for all visits where laboratory assessments will be performed. Participants should also abstain from taking biotin 72 hours prior to clinical laboratory testing.

o Thyroglobulin and anti-thyroglobulin testing only applicable for participants who have undergone total thyroidectomy for treatment of thyroid cancer.

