2.1. Study Rationale

This study will evaluate the safe and effective dose conversion from synthetic T4 therapy to Armour Thyroid therapy in participants who are euthyroid on a stable dose of synthetic T4. This study is designed to demonstrate that treatment with matching doses of Armour Thyroid is noninferior to treatment with synthetic T4, specifically in reference to euthyroid status as determined by TSH measurements. In addition, this study will demonstrate the safe and tolerable use of matching doses of Armour Thyroid to synthetic T4 in hypothyroid participants. Symptoms of hypothyroidism will be monitored as exploratory endpoints to evaluate potential differences between Armour Thyroid and synthetic T4.

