9.4.1.4. Estimand Framework for Primary Endpoint

Population

The target study population comprises previously hypothyroid patients who are presently euthyroid on a stable dose of synthetic T4 at the time of randomization, and who also meet the inclusion and exclusion criteria as specified in Sections 5.1 and 5.2, respectively.

The analysis population is the ITT population as defined in Section 9.3.

Variable

The variable is the primary efficacy endpoint, a sustained TSH responder endpoint defined as the TSH value within the normal reference range both at the end of Titration Period and at the end of the Stabilization Period.

Accounting for Intercurrent Events

Intercurrent events and their handling rules are as follows.

- Participants who discontinue study treatment due to any reason will have their data collected after discontinuation of study treatment and included in the study database and analysis, whenever possible.
- If a participant is missing TSH values either at the end of Titration Period or at the end of the Stabilization Period, the participant will be considered a TSH non-responder for the study.

Population-level Summary

The population-level summary will be a 2-sided 95% confidence interval in stratified proportion difference for the primary study responder endpoint.

The estimand framework for the secondary endpoint will be handled using the same approach as described for the primary.

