**6.2**

**LOW BASELINE TOTAL T3 SYMPTOMATIC SUBSET OF ITT POPULATION (ITT-T3)**

The low baseline total T3 symptomatic Population (abbreviated as ITT-T3 Population) will consist of all participants in the ITT Population who had a baseline total T3 < 87 ng/dL and a ThyPRO hypothyroidism symptom scale > 0.

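### SAP Table 4-1 does not mark ThyPRO at Early Termination, so participants who leave early give no exit symptom score

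*SAP*

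**What the plan says.** SAP Table 4-1 has eleven columns: ten visits (1, 2, 3a, 3b, 4a, 4b, 5a, 5b, 6, 7) and Early Termination. The row "Thyroid symptom questionnaire (ThyPRO Questionnaire" is marked at seven visits and is blank at 3b, 4b, 5b and Early Termination. No footnote adds it at Early Termination.

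Two related rows, "Serum TSH, T4, T3, FT3, FT4 (Thyroid-related assessments" and "Evaluation of thyroid clinical status", have the same seven marks plus one at Early Termination. Footnote l says of the second: "This includes evaluation of hypothyroid symptoms, which will be documented in the eCRF".

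Protocol 2.1 gives the role of symptoms: "Symptoms of hypothyroidism will be monitored as exploratory endpoints to evaluate potential differences between Armour Thyroid and synthetic T4". SAP 6.2 uses the baseline ThyPRO score to define the ITT-T3 subset, as participants "who had a baseline total T3 < 87 ng/dL and a ThyPRO hypothyroidism symptom scale > 0". Protocol 7.1 and 7.2 send sites to the Schedule of Activities for what to collect when a participant discontinues.

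**The concern.** Someone who stops because of how they feel is a person whose symptom score matters. ThyPRO asks about the past four weeks and the scheduled forms are about six weeks apart, so no form covers the time between the last completed visit and exit.

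Other data at the Early Termination visit fill the gap only in part. Normal TSH does not stand in for symptoms: the protocol's Introduction describes patients with persistent symptoms despite TSH in range. The clinical status evaluation records hypothyroid symptoms but yields no score on the 13 ThyPRO scales. The visible scoring rules in SAP Appendix C deal with missing items, not with a missing questionnaire.

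At stake is how far the symptom comparison between arms must rest on an assumption about people who left, when one form at a visit already scheduled would give a direct observation.

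**Working it through.** **Step 1. Is the blank cell really in the Early Termination column?** The table was read from PDF, so the rows were counted cell by cell. Each row below has eleven cells.

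| Row of SAP Table 4-1 | Visits marked | Early Termination |
|---|---|---|
| ThyPRO | 1, 2, 3a, 4a, 5a, 6, 7 | blank |
| TSH and thyroid hormones | same seven | marked |
| Thyroid clinical status | same seven | marked |
| PK blood samples | 2, 7 | blank |
| Physical examination | 1, 7 | marked |
| Adverse events | all ten | marked |

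The PK row is the anchor. Footnote k says "PK samples will be collected pre-dose and 2 hour (± 30 minutes) post-dose at Visits 2 and 7", which matches a mark in the tenth cell (Visit 7) and a blank eleventh (Early Termination). The ThyPRO row ends the same way, so a column shift does not explain its blank.

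**Step 2. What is lost, and what is kept?** By SAP Table 4-1 footnote e, Visits 5c, 5e and 5g repeat the assessments of Visit 5a, so ThyPRO continues about every six weeks in an extended Titration Period.
- Leaves before Visit 3a (Week 6): baseline score only.
- Leaves after Visit 3a: at least one post-baseline score; the exit score is missing.
- Stops treatment but stays in the study: can still complete ThyPRO at scheduled visits.

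**Step 3. How many people?** The visible text gives no dropout rate. Taking 5% to 20% as an assumption and the 284 participants in SAP 4.1:
- 284 × 0.05 = 14.2, about 14
- 284 × 0.10 = 28.4, about 28
- 284 × 0.15 = 42.6, about 43
- 284 × 0.20 = 56.8, about 57

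These are upper limits on the exit scores gained, because not everyone who leaves attends the visit.

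**Step 4. How large could the bias be?** Let p be the proportion leaving an arm and d the number of points by which leavers score worse than completers. A completers-only mean omits p × d, so the error in the between-arm difference is p₁d₁ − p₂d₂. All values of p and d below are assumptions.

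| Dropout, arm 1 v arm 2 | Deficit, arm 1 v arm 2 | Error (points, 0-100) |
|---|---|---|
| 10% v 10% | 10 v 10 | 1.0 − 1.0 = 0 |
| 10% v 10% | 15 v 10 | 1.5 − 1.0 = 0.5 |
| 20% v 10% | 10 v 10 | 2.0 − 1.0 = 1.0 |
| 20% v 10% | 15 v 15 | 3.0 − 1.5 = 1.5 |

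For scale, one raw step on the Hypothyroid Symptoms scale is 100/16 = 6.25 points for an individual. The visible text states no meaningful difference for a group mean.

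**The case against.** **The governing pages cannot be read.** The SAP restates the schedule; the protocol governs collection. Protocol 1.3, the Early Termination part of Appendix 8 (10.8.3) and the text of SAP 10.4 are not visible in the public copy, and SAP 12.0 leaves health outcomes analyses to a separate document. ThyPRO may be listed at Early Termination, or a rule for missed questionnaires given, in one of these. This stands, and is why the fix begins with a check.

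**One cell is thin evidence.** The serum pregnancy row of the same table is marked at every main visit and at Early Termination, while the footnote to the laboratory table in SAP 11.2 makes serum testing standard only at Visits 1 and 7. The PK anchor rules out a column shift; it does not rule out a dropped mark in the ThyPRO row. This also stands.

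**Symptom data are not absent for leavers.** A reader might infer that they have no symptom scores at all. The documents do not support that: earlier ThyPRO scores are kept and hypothyroid symptoms are recorded at Early Termination. Protocol 7.1 also asks for follow-up to the end of study, and Protocol 9.4.1.4 says that participants who stop treatment "will have their data collected after discontinuation of study treatment and included in the study database and analysis, whenever possible". That sentence belongs to the primary estimand, so applying it to ThyPRO is an inference.

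**The bias figure needs an analysis that nobody has stated.** No completers-only ThyPRO comparison appears in the visible text, and a method using the earlier scores would recover part of the loss. The figure is an illustration, not a forecast.

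**Conclusion.** The omission is confirmed in SAP Table 4-1 as printed, and its reach is narrow: the exit ThyPRO score of participants who leave early. It bears on the exploratory symptom comparison only. The primary and secondary TSH endpoints are untouched, and TSH is marked at Early Termination.

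The possible between-arm bias runs from about 0, with equal dropout and equal deterioration, to about 1 to 1.5 points under 20% v 10% dropout, a 10 to 15 point deficit and a completers-only analysis. None of those inputs comes from the documents.

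Two stronger readings are tempting. One is that participants will in fact leave because of symptoms, and more so in one arm; this is plausible, but the documents give no rate or reason that shows it. The other is that the ITT-T3 subset is compromised; its membership is fixed at baseline, so only the follow-up scores within it share the general gap. This is a cheap improvement to the plan rather than a defect in it.

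**What to change.** 1. Check SAP Table 4-1 against the protocol's own Schedule of Activities and the Early Termination section of Appendix 8. If ThyPRO is listed there, correct the SAP table and stop.
2. If it is not, mark ThyPRO in the Early Termination column of both schedules.
3. State that the Early Termination score is analysed as an observed value at its actual study day through the visit windows in SAP 16.2, and is not carried forward to Visit 7. Carrying it forward would replace one untestable assumption with another. SAP 16.2 uses the last non-missing value in a window, so an exit form on Day 55 would displace a Visit 3a form on Day 42 (both fall in Days 2 to 63). Say whether that is intended.
4. State how a missed ThyPRO questionnaire is handled, if the text that cannot be seen does not already do so.

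The cost is a minor amendment and one self-completed form at a visit that already includes laboratory tests, an ECG and a physical examination, so the visit is slightly longer. The change does nothing for those lost to follow-up or for those who left before it takes effect. SAP 4.1 says the enrollment increase has already been implemented, so some may have left; if few participants remain, disclosing the limitation may be all that is worthwhile.
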